5.3.5.14 Safety Biomarker Data

Adverse event reports will not be derived from safety biomarker data by the Sponsor, and safety biomarker data will not be included in the formal safety analyses for this study. In addition, safety biomarker data will not inform decisions on patient management.

5.4 IMMEDIATE REPORTING REQUIREMENTS FROM INVESTIGATOR TO SPONSOR

Certain events require immediate reporting to allow the Sponsor to take appropriate measures to address potential new risks in a clinical trial. The investigator must report such events to the Sponsor immediately; under no circumstances should reporting take place more than 24 hours after the investigator learns of the event. The following is a list of events that the investigator must report to the Sponsor within 24 hours after learning of the event, regardless of relationship to study drug:

- Serious adverse events (defined in Section 5.2.2; see Section 5.4.2 for details on reporting requirements)
- Adverse events of special interest (defined in Section 5.2.3; see Section 5.4.2 for details on reporting requirements)
- Pregnancies (see Section 5.4.3 for details on reporting requirements)

For serious adverse events and adverse events of special interest, the investigator must report new significant follow-up information to the Sponsor immediately (i.e., no more than 24 hours after becoming aware of the information). New significant information includes the following:

- New signs or symptoms or a change in the diagnosis
- Significant new diagnostic test results
- Change in causality based on new information
- Change in the event's outcome, including recovery
- Additional narrative information on the clinical course of the event

Investigators must also comply with local requirements for reporting serious adverse events to the local health authority and IRB/EC.

5.4.2 Reporting Requirements for Serious Adverse Events and Adverse Events of Special Interest

5.4.2.1 Events That Occur prior to Study Drug Initiation

After informed consent has been obtained but prior to initiation of study drug, only serious adverse events caused by a protocol-mandated intervention should be reported. The paper Clinical Trial Serious Adverse Event/Adverse Event of Special Interest Reporting Form provided to investigators should be completed and submitted to the Sponsor or its designee immediately (i.e., no more than 24 hours after learning of the event), either by faxing or by scanning and emailing the form using the fax number or email address provided to investigators.

5.4.2.2 Events That Occur after Study Drug Initiation

After initiation of study drug, serious adverse events and adverse events of special interest will be reported until 42 days after the final dose of study drug. Investigators should record all case details that can be gathered immediately (i.e., within 24 hours after learning of the event) on the Adverse Event eCRF and submit the report via the electronic data capture (EDC) system. A report will be generated and sent to Safety Risk Management by the EDC system.

In the event that the EDC system is unavailable, the paper Clinical Trial Serious Adverse Event/Adverse Event of Special Interest Reporting Form provided to investigators should be completed and submitted to the Sponsor or its designee immediately (i.e., no more than 24 hours after learning of the event), either by faxing or by scanning and emailing the form using the fax number or email address provided to investigators. Once the EDC system is available, all information will need to be entered and submitted via the EDC system.

Instructions for reporting serious adverse events that occur >42 days after the final dose of study treatment are provided in Section [5.6](#).

5.4.3 Reporting Requirements for Pregnancies

5.4.3.1 Pregnancies in Female Patients

Female patients of childbearing potential will be instructed to immediately inform the investigator if they become pregnant during the study or within 42 days after the final dose of study drug. A paper Clinical Trial Pregnancy Reporting Form should be completed and submitted to the Sponsor or its designee immediately (i.e., no more than 24 hours after learning of the pregnancy), either by faxing or by scanning and emailing the form using the fax number or email address provided to investigators. Pregnancy should not be recorded on the Adverse Event eCRF. The investigator should discontinue study drug and counsel the patient, discussing the risks of the pregnancy and the possible effects on the fetus. Monitoring of the patient should continue until conclusion of the pregnancy. Any serious adverse events associated with the pregnancy (e.g., an event in the fetus, an event in the mother during or after the pregnancy, or a congenital anomaly/birth defect in the child) should be reported on the Adverse Event eCRF. In addition, the investigator will submit a Clinical Trial Pregnancy Reporting Form when updated information on the course and outcome of the pregnancy becomes available.

5.4.3.2 Pregnancies in Female Partners of Male Patients

Male patients will be instructed through the Informed Consent Form to immediately inform the investigator if their partner becomes pregnant during the study or within 132 days after the final dose of study drug. The investigator should report the pregnancy on the paper Clinical Trial Pregnancy Reporting Form and submit the form to the Sponsor or its designee immediately (i.e., no more than 24 hours after learning of the pregnancy), either by faxing or by scanning and emailing the form using the fax number or email address provided to investigators. Attempts should be made to collect and report details of the course and outcome of any pregnancy in the partner of a male patient exposed to study drug. When permitted by the site, the pregnant partner would need to sign an Authorization for Use and Disclosure of Pregnancy Health Information to allow for follow-up on her pregnancy. If the authorization has been signed, the investigator should submit a Clinical Trial Pregnancy Reporting Form with additional information on the pregnant partner and the course and outcome of the pregnancy as it becomes available. An investigator who is contacted by the male patient or his pregnant partner may provide information on the risks of the pregnancy and the possible effects on the fetus, to support an informed decision in cooperation with the treating physician and/or obstetrician.

5.4.3.3 Abortions

A spontaneous abortion should be classified as a serious adverse event (as the Sponsor considers abortions to be medically significant), recorded on the Adverse Event eCRF, and reported to the Sponsor immediately (i.e., no more than 24 hours after learning of the event; see Section [5.4.2](#)).

If a therapeutic or elective abortion was performed because of an underlying maternal or embryofetal toxicity, the toxicity should be classified as a serious adverse event, recorded on the Adverse Event eCRF, and reported to the Sponsor immediately (i.e., no more than 24 hours after learning of the event; see Section 5.4.2). A therapeutic or elective abortion performed for reasons other than an underlying maternal or embryofetal toxicity is not considered an adverse event.

All abortions should be reported as pregnancy outcomes on the paper Clinical Trial Pregnancy Reporting Form.

5.4.3.4 Congenital Anomalies/Birth Defects

Any congenital anomaly/birth defect in a child born to a female patient exposed to study drug or the female partner of a male patient exposed to study drug should be classified as a serious adverse event, recorded on the Adverse Event eCRF, and reported to the Sponsor immediately (i.e., no more than 24 hours after learning of the event; see Section 5.4.2).

5.5 FOLLOW-UP OF PATIENTS AFTER ADVERSE EVENTS

5.5.1 Investigator Follow-Up

The investigator should follow each adverse event until the event has resolved to baseline grade or better, the event is assessed as stable by the investigator, the patient is lost to follow-up, or the patient withdraws consent. Every effort should be made to follow all serious adverse events considered to be related to study drug or trial-related procedures until a final outcome can be reported.

During the study period, resolution of adverse events (with dates) should be documented on the Adverse Event eCRF and in the patient's medical record to facilitate source data verification.

All pregnancies reported during the study should be followed until pregnancy outcome.

5.5.2 Sponsor Follow-Up

For serious adverse events, adverse events of special interest, and pregnancies, the Sponsor or a designee may follow up by telephone, fax, email, and/or a monitoring visit to obtain additional case details and outcome information (e.g., from hospital discharge summaries, consultant reports, autopsy reports) in order to perform an independent medical assessment of the reported case.

5.6 ADVERSE EVENTS THAT OCCUR AFTER THE ADVERSE EVENT REPORTING PERIOD

The Sponsor should be notified if the investigator becomes aware of any serious adverse event that occurs after the end of the adverse event reporting period (defined as 42 days after the final dose of study drug), if the event is believed to be related to prior study drug treatment. These events should be reported through use of the Adverse

Event eCRF. However, if the EDC system is not available, the investigator should report these events directly to the Sponsor or its designee, either by faxing or by scanning and emailing the paper Clinical Trial Serious Adverse Event/Adverse Event of Special Interest Reporting Form using the fax number or email address provided to investigators.

5.7 EXPEDITED REPORTING TO HEALTH AUTHORITIES, INVESTIGATORS, INSTITUTIONAL REVIEW BOARDS, AND ETHICS COMMITTEES

The Sponsor will promptly evaluate all serious adverse events and adverse events of special interest against cumulative product experience to identify and expeditiously communicate possible new safety findings to investigators, IRBs, ECs, and applicable health authorities based on applicable legislation.

To determine reporting requirements for single adverse event cases, the Sponsor will assess the expectedness of these events using the following reference document:

- BFKB8488A Investigator's Brochure

The Sponsor will compare the severity of each event and the cumulative event frequency reported for the study with the severity and frequency reported in the applicable reference document.

Reporting requirements will also be based on the investigator's assessment of causality and seriousness, with allowance for upgrading by the Sponsor as needed.

6. STATISTICAL CONSIDERATIONS AND ANALYSIS PLAN

The primary efficacy objective for this study is to evaluate the efficacy of BFKB8488A compared with placebo on the basis of the proportion of patients with resolution of NASH and no worsening of fibrosis. The primary and secondary efficacy analyses will be based on a modified intent-to-treat (mITT) approach. All patients who received at least one dose of study drug will be included in the mITT population, with patients grouped according to the treatment assigned at randomization. Analyses will be based on the final biopsy at Week 52 or MRI-PDFF measured over the course of the study.

The final analysis of data from the study will be performed when all patients have either: (i) completed the Week 52 visit and associated liver biopsy or (ii) withdrawn from the study prior to Week 52. The data analysis plan (DAP) will be specified prior to unblinding.

6.1 DETERMINATION OF SAMPLE SIZE

will be enrolled in *two cohorts*: 180 patients in the *fixed dose cohort* and [REDACTED]. In the four *fixed dose arms* patients are randomized in 1:3:3:2 ratio among 3 *active drug arms* and a *placebo arm*, with approximately 20 patients in the 50 mg BFKB8488A Q2W arm,

approximately 60 patients in both the 75 mg BFKB8488A Q2W and 100 mg BFKB8488A Q2W arm and approximately 40 in the placebo arm.

[REDACTED]

[REDACTED]

[REDACTED]

[REDACTED]

6.2 SUMMARIES OF CONDUCT OF STUDY

The number of patients who enroll, discontinue, or complete the study will be summarized. Reasons for premature study discontinuation will be listed and summarized. Enrollment and major protocol deviations will be listed and evaluated for their potential effects on the interpretation of study results.

6.3 SUMMARIES OF DEMOGRAPHIC AND BASELINE CHARACTERISTICS

Demographic and baseline characteristics (including age, sex, diabetes status, and important liver indicators of disease) will be summarized using means, standard deviations, medians, and ranges for continuous variables and proportions for categorical variables, as appropriate. Summaries will be presented overall and by treatment group.

6.4 EFFICACY ANALYSES

Efficacy analysis will be conducted for the modified intent-to-treat population, defined as all randomly allocated patients who received at least one dose of BFKB8488A or placebo. Sensitivity analyses of additional study populations (e.g., completers, or per protocol [excluding major protocol violators]) may also be performed for the primary endpoint or key secondary endpoints and will be detailed in the DAP. Statistical tests will be conducted at the 0.05 significance level for the modified intent-to-treat (mITT) population. No multiple testing- adjustment is planned. Further details will be specified in the DAP prior to unblinding.

6.4.1 Primary Efficacy Endpoint

The primary efficacy endpoint for this study is resolution of NASH with no worsening of fibrosis at Week 52 as determined by histology as defined in Section 2.1.1. The primary endpoint will be compared between each of the two fixed BFKB8488A arms and the single variable dose arm of BFKB8488A against the pooled placebo arms using an appropriate method such as the Cochran-Mantel-Haenszel test statistic, stratified by the factors used at randomization. Reporting details and methodology including missing data handling will be specified in the DAP.

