Investigational Medicinal Products

Test Product (Investigational Drug)

BFKB8488A will be given at dose levels 50 mg, 75 mg, 100 mg, and [REDACTED] by subcutaneous injection every 2 weeks for 52 weeks.

Comparator

Placebo will be given by subcutaneous injection every 2 weeks for 52 weeks.

Statistical Methods

Primary Analysis

The primary efficacy objective for this study is to evaluate the efficacy of BFKB8488A compared with placebo on the basis of the proportion of patients with resolution of NASH and no worsening of fibrosis. The primary and secondary efficacy analyses will be based on a modified intent-to-treat (mITT) approach. All patients who received at least one dose of study drug will be included in the mITT population, with patients grouped according to the treatment assigned at randomization. Analyses will be based on the final biopsy at Week 52 or MRI-PDFF measured over the course of the study.

The final analysis of data from the study will be performed when all patients have either: (i) completed the Week 52 visit and associated liver biopsy or (ii) withdrawn from the study prior to Week 52. The data analysis plan (DAP) will be specified prior to unblinding.

Determination of Sample Size

[REDACTED] will be enrolled in two cohorts: 180 patients in the fixed dose cohort and [REDACTED]. In the four fixed dose arms patients are randomized in 1:3:3:2 ratio among 3 active drug arms and a placebo arm, with approximately 20 patients in the 50 mg BFKB8488A Q2W arm, approximately 60 patients in both the 75 mg BFKB8488A Q2W and 100 mg BFKB8488A Q2W arm and approximately 40 in the placebo arm. [REDACTED]

[REDACTED]. There is $\geq 90\%$ power to detect a 30% increase in resolution of NASH, assuming a 15% placebo rate, a type I error rate of 0.05, a two sided test of proportions and 10% lost to follow-up comparing any single arm, with the exception of the 50-mg arm, to the pooled placebo arms. The 50-mg arm, under the same assumptions and a sample size of 20, will have 76% power. The fixed dose cohort alone, under the same assumptions, has a power of 87% comparing the 75-mg arm or 100-mg arm to the placebo arm and a power of 66% for the 50-mg arm.

Interim Analyses

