2.1 EFFICACY OBJECTIVES

2.1.1 Primary Efficacy Objective

The primary efficacy objective for this study is to evaluate the efficacy of BFKB8488A compared with placebo on the basis of the following endpoint:

- Proportion of patients with resolution of NASH on overall histopathological reading, without worsening of fibrosis at Week 52. Resolution of NASH is defined as a NAS of 0–1 for inflammation, 0 for ballooning, and any value for steatosis as determined by a central reader. Worsening of fibrosis is defined as any increase in NASH Clinical Research Network (CRN) fibrosis stage as determined by a central reader.

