2.6 HEALTH STATUS UTILITY OBJECTIVE

The exploratory health status utility objective for this study is to assess the patient perspective on response to BFKB8488A on the basis of the following endpoint:

- Change from baseline in Appetite Sensations Visual Analogue Scale (VAS) scores at specified timepoints

3. **STUDY DESIGN**

3.1 **DESCRIPTION OF THE STUDY**

This is a Phase II, randomized, parallel-group, double-blind, placebo-controlled, multicenter study to evaluate the efficacy, safety, and pharmacokinetics of BFKB8488A compared with placebo in patients with NASH. [REDACTED]

[REDACTED] as determined by the Sponsor's Internal Monitoring Committee [IMC]; see Section 3.1.2 for additional details) will be enrolled at multiple investigational sites across the globe. Patients will be randomly assigned to receive either BFKB8488A or placebo *in the fixed dosing cohort* [REDACTED]

[REDACTED] In the fixed dose arms, patients will be randomly assigned to receive BFKB8488A 50 mg, BFKB8488A 75 mg, BFKB8488A 100 mg, or placebo. [REDACTED]

[REDACTED] Randomized patients will be stratified by diabetes status and fibrosis stage (F1 vs. F2/F3). A maximum of up to approximately 20% of patients with F1 will be enrolled in this study.

The study will consist of a screening period (up to 8 weeks; including an initial screening and a main screening), a subsequent 52-week treatment period, and a 6-week safety follow-up period. The total duration of the study for each patient will be approximately 66 weeks.

During screening (up to 8 weeks), eligibility screening assessments should be completed as early as possible. All eligibility assessments must be completed within the 8-week screening period with the exception of delays in laboratory (including biopsy) and MRI reporting or due to unforeseen scheduling issues. All eligibility assessments should be completed prior to randomization.

Patients will be required to undergo a liver biopsy prior to randomization in order to confirm diagnosis of NASH. An archival liver sample collected within 6 months prior to randomization may be used provided it meets eligibility requirements (see Section 4.1); otherwise, a fresh biopsy will be taken during the screening period.

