Exploratory research on safety biomarkers may be conducted to support future drug development. Research may include further characterization of a safety biomarker or identification of safety biomarkers that are associated with susceptibility to developing adverse events or can lead to improved adverse event monitoring or investigation. Adverse event reports will not be derived from safety biomarker data by the Sponsor, and safety biomarker data will not be included in the formal safety analyses for this study. In addition, safety biomarker data will not inform decisions on patient management.

4. **MATERIALS AND METHODS**

4.1 **PATIENTS**

[REDACTED] as determined by the IMC, see Section 3.1.2 for additional details).

4.1.1 **Inclusion Criteria**

- Signed Informed Consent Form

[REDACTED]

- AST \geq 20
- FibroScan® fibrosis result \geq 7.0 kilopascals (kPa)
- FibroScan® controlled attenuation parameter (CAP) \geq 285 decibels per meter (dB/m)

Patients must meet the following criteria during the main screening for study entry:

- Age \geq 18 and \leq 75 years at time of signing Informed Consent Form
- Ability to comply with the study protocol (including ability to safely obtain a liver biopsy if needed), in the investigator's judgment
- Hepatic steatosis on MRI (\geq 8% average liver PDFF) prior to randomization
- Confirmed diagnosis of NASH as documented through central testing of a representative liver sample performed no more than 6 months before randomization, with a NAS greater than or equal to 4 with at least 1 point each in inflammation and ballooning along with a NASH CRN fibrosis score between F1 and F3 (a maximum of approximately 20% of patients with F1 will be enrolled). The biopsy must be performed while the patient is not on any treatment prescribed for the purpose of this study or on any investigational therapy for the treatment of NASH.

If an archival liver sample is unavailable or does not meet eligibility criteria, liver tissue must be obtained from a biopsy performed at screening.

- For women of childbearing potential: agreement to remain abstinent (refrain from heterosexual intercourse) or use contraceptive measures, and agreement to refrain from donating eggs, as defined below:

Women must remain abstinent or use a contraceptive method with a failure rate of <1% per year during the treatment period and for at least 42 days after the final dose of study drug. Women must refrain from donating eggs during this same period.

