4.5.10.1 NAFLD Activity Score

The NAS will be assessed at screening and at end-of-treatment.

NAS is a system of histologic evaluation that includes the disease spectrum from NAFLD to NASH. NAS assesses three types of lesions that comprise-grade steatosis, lobular inflammation, and ballooning (Kleiner et al. 2005). The aggregate NAS is the unweighted sum of the scores of each component of the NAS (steatosis [0–3], lobular inflammation [0–3], ballooning [0–2]).

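### The primary test named in 6.4.1 is valid but makes no use of baseline ballooning and inflammation grade; prespecify both as covariates before unblinding

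*Combined protocol and SAP*

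**What the plan says.** Section 6.4.1 compares active arms with the pooled placebo arms "using an appropriate method such as the Cochran-Mantel-Haenszel test statistic, stratified by the factors used at randomization", and leaves methodology and reporting details to the DAP. Sections 6 and 6.4 say the DAP will be specified before unblinding.

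Section 3.1 gives the factors: "Randomized patients will be stratified by diabetes status and fibrosis stage (F1 vs. F2/F3". With two binary factors there are four strata. It adds: "A maximum of up to approximately 20% of patients with F1 will be enrolled in this study".

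Section 2.1.1 sets the target: "Resolution of NASH is defined as a NAS of 0–1 for inflammation, 0 for ballooning", with any steatosis grade allowed and no increase in fibrosis stage. Section 4.1.1 sets entry by central testing of the biopsy, "with a NAS greater than or equal to 4 with at least 1 point each in inflammation and ballooning". Under 4.5.10.1, "The aggregate NAS is the unweighted sum of the scores of each component of the NAS"; inflammation is scored 0 to 3 and ballooning 0 to 2.

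The Synopsis (Determination of Sample Size) computes power for a 30-point increase "assuming a 15% placebo rate, a type I error rate of 0.05, a two sided test of proportions and 10% lost to follow-up". It gives 87% for 75 mg or 100 mg, and 66% for 50 mg, against the fixed-dose placebo arm. Section 6.3 summarises baseline liver indicators by arm. Section 6.4.2 analyses the histology secondary endpoints in the same way as the primary.

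**The concern.** The endpoint is an absolute state at Week 52, but patients start at different distances from it. The two grades that fix that distance are known before treatment for every eligible patient. Neither is a stratification factor, and neither is named in the primary comparison. Diabetes status and fibrosis stratum do not measure the distance.

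At stake are some precision, obtainable without further biopsies, and protection against a chance imbalance in baseline activity, which the plan would tabulate but the named test would not adjust for. If the covariates are to be used, they must be fixed in advance; adding them after an imbalance has been seen would not be credible.

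**Working it through.** **Distance to response.** Patients enter with ballooning 1 or 2 and inflammation 1 to 3. They need ballooning 0 and inflammation 0 or 1. Points needed = ballooning + max(0, inflammation − 1): at least 1 + 0 = 1, at most 2 + 2 = 4.

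**The plan's own power.** Inputs: 15% against 45%, two-sided 0.05, 10% loss, so 60, 40 and 20 become 54, 36 and 18. Power = Φ[(0.30 − 1.96·SE0)/SE1], where SE0 = √[p̄(1 − p̄)(1/n0 + 1/n1)] and SE1 = √[p0(1 − p0)/n0 + p1(1 − p1)/n1].

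- 54 v 36: p̄ = (24.3 + 5.4)/90 = 0.330, SE0 = 0.1012, SE1 = 0.0901; Φ(1.13) = 87.0%. Stated: 87%.
- 18 v 36: p̄ = (8.1 + 5.4)/54 = 0.250, SE0 = 0.1250, SE1 = 0.1315; Φ(0.418) = 66.2%. Stated: 66%.

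No covariate enters either figure.

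**Power with the grades as main effects.** The documents give neither the grade distribution nor its prognostic strength. Assumed: ballooning 2 in 60%; inflammation 1/2/3 in 30/55/15%; diabetes in 50% and F1 in 20%, neither prognostic. Odds ratios are against resolution, for ballooning 2 v 1 and per inflammation grade. Marginal rates were held at 15% and 45%. Each cell rests on 6,000 simulated trials (Monte Carlo standard error near 87%: √(0.87 × 0.13/6,000) = 0.4 points). It shows the power (%) of a logistic score test with diabetes and fibrosis stratum, then with both grades added.

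| Odds ratios (ballooning/inflammation) | 54 v 36 | 18 v 36 | 54 v 54 |
|---|---|---|---|
| 1/1 | 87.2 → 86.9 | 68.1 → 67.1 | 93.6 → 93.3 |
| 1.5/1.5 | 87.3 → 87.8 | 67.2 → 67.4 | 93.8 → 94.0 |
| 2/1.5 | 86.9 → 87.9 | 66.6 → 67.4 | 93.4 → 93.9 |
| 3/2 | 87.9 → 90.2 | 66.9 → 69.4 | 93.9 → 95.5 |
| 5/3 | 87.8 → 92.5 | 67.0 → 73.5 | 94.2 → 97.2 |

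The last column assumes 60 pooled placebo patients. The true number is blacked out; 60 fits the 10:3 ratio in 3.3.3 if the total is 260 (200:60).

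**Type I error of the adjusted test.** The table uses no small-sample correction. For 54 v 36 under the null, the test with the grades rejected in 5.3% to 5.8% of trials, against 4.9% to 5.5% without them. With the variance multiplied by n/(n − 5), ballooning 2 in 50%, and odds ratios from 2/1.4 to 5/2.5, power was 88% to 92% against 86% to 87% for four-stratum CMH, with type I error of 4.4% to 5.1%. A further run for 54 v 36 gave gains of about 0 points up to 2/1.5, about 3 at 3/2 and about 4 at 5/2.5, with type I error across all settings of 4.2% to 5.3%.

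**Form of adjustment.** Using the grades as extra CMH strata for 54 v 36 (20,000 runs) gave:

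- 4 strata: about 86%
- ballooning added (8 strata): 84% to 88%
- ballooning and two-level inflammation (16 strata): 81% to 86%
- ballooning and three-level inflammation (24 strata): 78% to 85%

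The 16- and 24-stratum versions gained nothing at any strength. At 20% F1, about 0.2 × 90 = 18 patients would be spread over 12 of the 24 cells.

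**Validity and chance imbalance.** Four-stratum CMH rejected in 4.5% to 4.9% of null trials. With ballooning 2 in 60%, the between-arm difference in its share has SD √[0.24(1/36 + 1/54)] = 10.5 points for 54 v 36 and √[0.24(1/36 + 1/18)] = 14.1 points for 18 v 36. It exceeds 15 points in about 15% and 28% of trials. A 15-point imbalance moves an arm's response rate by 0.15 × the gap in response between ballooning 1 and 2:

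- at a 15% rate, from 0.15 × (18.2 − 12.9) = 0.8 points (odds ratio 1.5) to 0.15 × (27.1 − 6.9) = 3.0 points (odds ratio 5)
- at a 45% rate, from 0.15 × (51.0 − 41.0) = 1.5 to 0.15 × (67.9 − 29.7) = 5.7 points

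**The case against.** Stratifying by the randomization factors is standard and valid. Randomization and the test's own error rate already allow for chance imbalance, and the shift from a 15-point imbalance is small beside a planned 30-point difference. The gain depends on a prognostic strength that the documents do not give. Sampling error in biopsies, which 4.5.9 acknowledges, and baseline tissue up to 6 months old would both weaken it. CMH is only an example, and the DAP may already include the grades. The proposed model is more complex, with about 0.15 × 36 = 5.4 expected placebo responders in the fixed-dose cohort, and it was not simulated for the variable-dose arm.

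Most of this stands and limits the size of the point. It does not remove it: the grades define the distance to the endpoint, they are already collected, and the open wording is a reason to settle the matter before unblinding.

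A reader might infer that the trial loses power against its stated 87% and 66%. It does not: those figures take no credit for covariates. A reader might also infer that leaving the grades out biases the comparison or inflates type I error. The null runs show otherwise. Nor can the 50-mg arm carry the argument: 6.4.1 refers to two fixed-dose arms where 3.1 has three, so it is unclear whether that arm is formally tested.

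**Conclusion.** The point holds as an efficiency gain that the plan could take, not as an error in it. For 54 v 36, the gain is about 0 to 1 point of power with weak to moderate prognostic grades, 2 to 3 points at about 3/2, and 4 to 5 points only when they are strongly prognostic. Against a pooled placebo group of 60, if that is its size, the uncorrected runs give at most 3 points (94.2% to 97.2%). With a small-sample variance factor, type I error stays near 5%. If the grades carry no information, the cost is a fraction of a point for 54 v 36 and about 1 point for 18 v 36.

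These sizes rest on the assumed grade distribution and odds ratios. The documents do not show that the sponsor decided against covariates, only that the protocol names none beyond the two stratification factors.

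**What to change.** In 6.4.1 and the DAP, before unblinding:

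- Make the primary comparison covariate-adjusted, with treatment arm, diabetes status, fibrosis stratum, baseline ballooning grade and baseline lobular inflammation grade as main effects. A logistic score test of each tested arm against pooled placebo, with a small-sample variance factor defined in the DAP, would serve. Confirm its type I error by simulation at the actual arm sizes, including the variable-dose arm.
- Do not cross both grades into the CMH strata.
- Report a standardised risk difference.
- Keep the four-stratum CMH test as a sensitivity analysis.
- In 6.4.2, choose baseline covariates suited to each histology endpoint. As written, 6.4.2 would carry over the primary model, but the rationale does not transfer. The NAS endpoint is a reduction from baseline, so higher grades leave more room to improve; fibrosis improvement depends on baseline fibrosis stage.

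The cost is wording and a slightly more complex model. No new data, patients or procedures are needed.
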